Energy Expenditure of Remote Exercise Sessions (optional). Energy expenditure of the remote sessions will be assessed in a volunteer sample using a previously validated portable, open-circuit indirect calorimeter (Cosmed, Italy) which measures breath-by-breath ventilation, expired oxygen, and carbon dioxide. The flow turbine will be calibrated using a 3.0-L syringe. The lightweight (~1.5 kg) portable system will be attached by a harness around the waist and shoulders of the participant before each assessment. During exercise sessions, participants will breathe into a facemask that directs air into the unit housing the O₂ and CO₂ analyzers. Data will be retrieved for analysis via a serial port interface and software provided with the calorimeter, and aggregated over 20-second epochs for the calculation of 1-min averages. MET levels will be age corrected using the Schofield equation (88) as recommended by McMurray et al (89). Participants will be asked to wear wrist ActiGraphs during the assessment for comparison of physical activity levels between devices.

SAMPLE SIZE, STATISTICAL METHODS, AND POWER CALCULATION

Power/sample size. The mean 6 mo. weight loss in our completed trial in adults with MRDs, using a protocol similar to the *IH* arm in the proposed trial, i.e., eSLD and behavioral counseling delivered by monthly home visits, was 5.5 kg (58). This does not reach the 8.5 kg (~5%) average 6 mo. weight loss defined as clinically meaningful by current weight management guidelines (53). We expect 6 mo. weight loss in the *GR* arm, which includes weekly group counseling and group exercise, will reach or exceed 8.5 kg. To detect a clinically meaningful difference of 3 kg (133, 176-180) in 6 mos. weight loss between the *IH* and *GR* arms, with 80% power and a type 1 error rate of 0.05, assuming a common standard deviation of 6 kg, will require 64 participants/group. Secondarily, we will have 70% power to detect a 3 kg difference in a completer analysis with an attrition rate of 20%; however, we expect attrition will be lower based on experience (71, 78, 181), and our use of retention/incentive strategies to minimize loss to follow-up. Thus, a sample of 64/group will provide adequate power for both our primary intent-to-treat analysis with imputed missing data (power = 80%) and our secondary completer only analysis (70%).

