Missing Data/ imputation. All analyses will be based on intent-to-treat principles and missing data for analyses of the primary aim will be imputed; therefore, oversampling for attrition is not needed. We will determine if the proportion of participants lost to follow-up differs by treatment. If so, we will determine if there are differences in demographic characteristics (sex, age, baseline weight, $p < 0.05$) between completers and those lost to follow-up. If missing data are related to treatment and/or these demographic characteristics, we will use model based multiple imputation; otherwise, we will use traditional multiple imputation. Statistical analysis will be completed with SAS version 9.4 or higher.

REFERENCES

2. Brault MW. Americans with Disabilities: 2010 Current Population Reports. Washington, DC: US Census Bureau; 2012. p. 40-131.

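### The 80% power claimed for the imputed primary analysis is the power with no missing 6-month weights; with weakly predictive imputation variables it is about 76% at 10% loss and 71% at 20%

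*Combined protocol and SAP*

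**What the plan says.** The Power/sample size paragraph sets the target ("To detect a clinically meaningful difference of 3 kg") and derives the sample size: "with 80% power and a type 1 error rate of 0.05, assuming a common standard deviation of 6 kg, will require 64 participants/group". That derivation has no term for missing weights. The paragraph then considers attrition, but for the completer analysis only: "we will have 70% power to detect a 3 kg difference in a completer analysis with an attrition rate of 20"%. It adds that "we expect attrition will be lower based on experience", without giving a lower figure. It closes by claiming "adequate power for both our primary intent-to-treat analysis with imputed missing data (power = 80%) and our secondary completer only analysis (70"%).

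The Missing Data/imputation paragraph draws the consequence for enrolment: "missing data for analyses of the primary aim will be imputed; therefore, oversampling for attrition is not needed". On method, it tests whether loss differs by arm and then, if so, whether sex, age or baseline weight differ between completers and those lost. If missingness is related to arm and/or those characteristics, "we will use model based multiple imputation; otherwise, we will use traditional multiple imputation". Neither type of imputation is defined, and no auxiliary variable or assumed correlation with weight loss is given.

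**The concern.** The two analyses start from the same observed weights. At 20% loss about 51 of 64 participants per arm have a 6-month weight, whether the rest are left out or imputed. The plan lowers the completer analysis to 70% for this reason but leaves the imputed analysis at the no-loss figure.

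That would be right only if imputation replaced the missing information in full. Valid multiple imputation adds the between-imputation variance to the standard error, so the price of the missing weights is still paid. Treating imputed values as if they had been measured would give an apparent 128 observations, but it would understate the standard error, and it is not the method the plan names.

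At stake are the stated chance of missing a true 3 kg difference in the primary analysis and the only reason the plan gives for not allowing for attrition in the sample size.

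**Working it through.** **Inputs from the Power/sample size paragraph.** Difference δ = 3 kg; common SD σ = 6 kg; type 1 error 0.05; n = 64 per arm; attrition 20%. The Analysis plans paragraph gives the test, a two-sample t-test. Sidedness is not stated. Two-sided is used because it reproduces 64 per arm; one-sided 0.05 would need only 50 (normal approximation).

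**Assumptions.** Loss of 5%, 10% and 15% is illustrative, since the plan gives only 20%. Loss is equal in both arms and completely at random.

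**Step 1: reproduce the plan's figures.** Power comes from the noncentral t distribution with 2n − 2 degrees of freedom and noncentrality δ / (σ√(2/n)).
- n = 64: noncentrality 3 / (6 × √(2/64)) = 2.83, power 80.1%. At n = 63 it is 79.5%, so 64 is the correct answer with complete data.
- n = 51 (20% loss, rounded down): power 70.6%. The plan's 70% for completers is correct.

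**Step 2: power of the imputed analysis when the imputation variables carry little information.** The information is then close to that of the observed weights, 64 × (1 − loss) per arm. Enrolment needed to keep 64 observed is 64 / (1 − loss), rounded up.

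| Loss | Effective n per arm | Power for 3 kg | Difference detectable with 80% power | Enrolment per arm to keep 64 observed |
|---|---|---|---|---|
| 0% | 64.0 | 80.1% | 2.99 kg | 64 |
| 5% | 60.8 | 78.1% | 3.07 kg | 68 |
| 10% | 57.6 | 75.8% | 3.16 kg | 72 |
| 15% | 54.4 | 73.4% | 3.25 kg | 76 |
| 20% | 51.2 | 70.7% | 3.35 kg | 80 |

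**Step 3: check by simulation.** Proper multiple imputation was simulated with arm and an uninformative covariate in the model, Rubin's rules with small-sample degrees of freedom, and 4,000 trials per setting (Monte Carlo standard error about 0.7 points).
- With 50 imputations and 3, 6, 10 or 13 weights lost per arm, power was 78.0%, 74.6%, 72.2% and 69.6%. The completer t-test on the same data gave 78.3%, 74.9%, 72.9% and 70.3%.
- A separate run with 20 imputations gave 80.3% at no loss, 75.8% at 10% and 70.3% at 20%.

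The imputed and completer analyses have practically the same power, and both agree with the formula within simulation error.

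**Step 4: allow for informative auxiliary variables.** Suppose auxiliaries explain a share R² of the variance of weight change and are available for every participant lost. Then n_eff = 1 / (R²/64 + (1 − R²)/n_obs), with n_obs = 51.2 at 20% loss.
- R² = 0.5: 1 / (0.5/64 + 0.5/51.2) = 56.9, power 75.3%.
- R² = 0.8: 1 / (0.8/64 + 0.2/51.2) = 61.0, power 78.2%.
- At 10% loss (n_obs = 57.6) the same R² values give 78.0% and 79.3%.

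**The case against.** The strongest reply is that the loss may be small and partly recoverable. The plan expects attrition below 20% and cites earlier trials for this. It schedules weights at 12 and 18 months, which could inform imputation for someone who misses month 6 and returns, and it collects attendance and adherence data. This stands as a qualification on size: the 76% and 71% are for weak imputation variables. It does not rescue the 80%. No lower attrition figure is given, no auxiliary variable is named for the imputation, permanent dropouts have no later weights, and even R² = 0.8 with complete auxiliary data stays below 80% at 10% and 20% loss.

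A second reply is that the plan already discloses 70% at 20% loss and calls it adequate. It does, but for the secondary analysis; the reader is told that the primary analysis is protected from that loss. If about 70% is adequate, stating it for the primary analysis costs nothing.

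Third, the correction changes no estimate, confidence interval or type 1 error, and with a January 2024 approval date and a first cohort run under COVID-19 conditions, recruitment may be well advanced. The documents do not give enrolment status. That is why no change in sample size is proposed. It is also fair that a very small loss is immaterial (63 per arm still rounds to 80%), and that the SD assumption matters as much: with no loss, an SD of 6.25 or 6.5 kg gives 76.9% or 73.6%.

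Finally, the data-dependent choice of imputation method is a specification matter and does not cause the power error. That is correct, and it is treated as secondary here.

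**Conclusion.** The concern holds. The plan's 64 per arm and its 70% for completers are arithmetically right. The error is to give the complete-data 80% to an analysis with missing weights, and to infer from imputation that attrition needs no allowance.

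At the plan's own 20% attrition figure the chance of missing a true 3 kg difference is about 29%, and at 10% about 24%, against the 20% implied. These figures rest on a two-sided test, SD 6 kg, loss completely at random and equal by arm, and weakly predictive imputation variables. Better auxiliaries would narrow the shortfall without closing it. The point should be fixed, but the design survives it.

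**What to change.** 1. In Power/sample size, describe the 80% as the power with all 6-month weights observed. State the power of the imputed primary analysis as about 70% at 20% attrition and about 76% at 10%, or equivalently as 80% for a difference of about 3.35 kg at 20% loss. Say that these figures assume weakly predictive imputation variables.
2. In Missing Data/imputation, delete the clause saying that oversampling is not needed.
3. Secondary, and not needed to correct the power figure: replace the test-dependent choice between two undefined imputation methods with one prespecified multiple imputation model that always includes arm, baseline weight, sex and age. As written, it is unclear whether demographic differences alone can trigger the first method, because they are examined only if loss differs by arm. Home-scale weights could be added as auxiliaries if the sponsor confirms that they are captured in the study data, but the stated power should not rely on them.

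The cost is wording in two paragraphs and a less favourable power statement. The sample size, visits and t-test are unchanged.

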group behavioral counseling in 16 overweight/obese adults with chronic spinal cord injury (SCI, ≥ 1 yr., age ~ 44 yrs., 100% non-ambulatory) with a 12 wk. follow-up. Results indicated small, but statistically significant weight loss at both 12 (-3.8%, $p < 0.0004$) and 24 wks. (-3.0%, $p < 0.01$). Betts & Froehlich-Grobe (56) recently reported -4.8% weight loss in a 20-wk. trial in a small sample (n=10) of adults (age ~ 49 yrs.), with MRDs (80% non-ambulatory) using the Diabetes Prevention Group Lifestyle Balance program delivered by weekly group phone calls (1-12 wks.), with 3 additional calls over the following 8 wks. Radomski et al (57) reported a median weight loss of 5.7% in a small sample of adults (n=10, age ~ 53 yrs.) with SCI (100% non-ambulatory) following a 12 wk. exercise and education intervention consisting of individualized diet and exercise recommendations, weekly on-site group nutrition and exercise education, and twice weekly exercise sessions (both group and individual). Our group recently published results from a 12 mo. trial (6 mos. weight loss, 6 mos. maintenance, NIDRR 133G090230, [name], PI) in a sample of 126 low income ($\sim 83\%$ unemployed), overweight/obese (BMI ~ 44 kg/m 2), adults (age ~ 51 yrs.) with MRDs, 71% used wheelchair or an assistive device for walking (58). Participants were randomized to a behavioral weight loss intervention that included monthly home visits by a health educator and a reduced energy conventional meal plan, or an enhanced Stop Light Diet (eSLD; 1,200-1,500 kcal/d), self-monitoring (logs), and optional PA. The Stop Light Diet, developed for use in children (59), categorizes foods by energy content corresponding to a traffic light, i.e., red (eat sparingly), yellow (eat moderately), and green (eat freely). We enhanced the SLD by encouraging daily consumption of 2 portion-controlled meals (≤ 300 kcal each), 2 high volume low energy shakes (100 kcal each), and \geq five 1-cup servings of fruits/vegetables. Mean percent weight loss was significantly greater in the eSLD compared with the meal plan groups at 6 mos. (eSLD = -4.1%, meal plan = -2.3%, $p = 0.024$) and 12 mos. (eSLD = -6.2%, meal plan = -0.6%, $p = 0.005$). The percentage of randomized participants achieving $\geq 5\%$ weight loss at 6 mos. did not differ by group (eSLD = 36%, meal plan = 23%, $p = 0.15$). However, the percentage of participants losing $\geq 5\%$ of baseline weight at 12 mos. was significantly higher in the eSLD (36%) compared with the meal plan groups (13%, $p = 0.003$).

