We propose a 2-arm randomized trial (group remote (*GR*) vs. individual home visit (*IH*)) using intent-to-treat principles, to compare body weight following weight loss (6 mos.) and maintenance (18 mos.) in overweight/obese adults with MRDs. interventions will be delivered by trained health educators and will include behavioral sessions, a reduced energy diet (eSLD), increased PA, and self-monitoring of weight using electronic scales. The *GR* arm will be delivered via video conferencing (Zoom™ software) on a tablet computer (iPad mini) with self-monitoring of diet and PA using commercially available technologies. Participants in the *IH* arm will self-monitor diet and PA using paper and pencil records. Due to COVID-19, all Cohort 1 *IH* intervention meetings will be held by phone per CDC social distancing recommendations. Participants are asked to send pictures of the tracking sheets to the health educator prior to the phone meeting. The primary outcome (weight) will be assessed during home visits at baseline (mo. 0), following weight loss (6 mos.), during (12 mos.) and at the end of maintenance (18 mos.). Our group has experience with all proposed intervention components and outcome assessments from previously completed (44, 58, 71, 78, 88, 89) or on-going trials (DK83589, HD79642). The following design attributes, described in detail subsequently, ensure the scientific rigor of the proposed trial: 1) Randomized design with equal allocation to groups, with allocation assignment concealed. 2) Adequate statistical power to address the primary aim. 3) Strategies to ensure the recruitment of sufficient participants to achieve our desired sample size. 4) Retention/incentive strategies to reduce loss to follow-up. 5) Controlling for attention by maintaining equal contact in both groups. 6) Secondary/exploratory aims to maximize the use of data, e.g., analysis to examine the impact of process variables/participant characteristics on

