Analysis plans. *Primary aim* will use a 2-sample independent t-test to compare 6 mo. weight loss between the 2 intervention arms in both an intent-to-treat, and completer only analysis. Procedures for handling missing data are described below. We will examine the impact of baseline characteristics (age, sex, race/ethnicity, weight, type of MRD, wheelchair use, employment status, living situation, food shopping and preparation) on weight change using linear regression controlling for treatment. We will examine the main effects of each of these variables, as well as the potential interaction effect with treatment.

Secondary aim 1, a comparison of 18 mo. weight loss, will mirror the analysis for the primary aim. We will use a 2-sample t-test to compare weight change (0-18 mos.) between the 2 intervention arms. Mixed linear models will be used to compare weight change from 0-18 mos.

between intervention arms controlling for intervention arm and baseline weight. We anticipate greater loss to follow-up over time; however, we expect data to be missing at random. Under this assumption, mixed linear models will provide unbiased treatment comparisons. We will assume an autoregressive correlation structure of the dependent variable (weight) over time, and evaluate the potential for time-by-treatment interactions.

Secondary aim 2, a between arm comparison of the proportion of participants achieving $\geq 5\%$ weight loss (0-18 mos.) will be evaluated using a chi-square test. Participants without an 18 mo. weight will be classified as not meeting the $\geq 5\%$ weight loss goal. We will also examine the impact of baseline characteristics, as previously defined, on 18 mo. weight loss using logistic regression.

Secondary aims 3 and 4, between arm comparison of change in risk factors and quality of life (0-6 and 0-18 mos.) will be evaluated using a 2-sample t-test.

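### The 18-month mixed model fixes an autoregressive structure and rests unbiasedness on missing at random alone; under the usual equal-variance fit with baseline as covariate, neither its error rate nor its unbiasedness is secured

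*Combined protocol and SAP*

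**What the plan says.** All references are to the combined protocol and SAP.

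- **Analysis plans, Secondary aim 1.** The 18-month comparison has two analyses. The first is a t-test: "We will use a 2-sample t-test to compare weight change (0-18 mos.) between the 2 intervention arms". The second is a mixed linear model for weight change over 0-18 months, compared "between intervention arms controlling for intervention arm and baseline weight".
- **Covariance.** "We will assume an autoregressive correlation structure of the dependent variable (weight) over time". The plan does not say whether variances may differ by visit or whether baseline is also a response visit. It names no alternative structure, no fallback and no robust standard error. Time-by-treatment interaction is something to be evaluated, not a fixed term.
- **Missing data in this model.** "We anticipate greater loss to follow-up over time; however, we expect data to be missing at random". The next sentence reads: "Under this assumption, mixed linear models will provide unbiased treatment comparisons".
- **Power/sample size.** The calculation is for 6-month weight loss, "assuming a common standard deviation of 6 kg". This is the only SD in the plan.
- **Study type and design.** Weight is measured at months 0, 6, 12 and 18.
- **Missing Data/imputation.** Imputation is committed explicitly to the primary aim. For later missingness, the mixed model is the stated answer.

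**The concern.** Two things are left unsecured.

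First, missing at random is not enough. When data are missing, a likelihood-based mixed model fills the gap through its mean and covariance model. If the covariance is wrong, the month-18 contrast can be biased even though the data are missing at random.

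Second, the commonly fitted AR(1) has one variance for all visits. If the spread of weight given baseline grows between months 6 and 18, that single variance is too small at month 18. The standard error is then too small, and the test rejects too often.

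At stake is the longitudinal half of the first secondary aim, in a trial that itself expects loss to increase with time.

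**Working it through.** **1. The plan's own figure.** Difference 3 kg, SD 6 kg, two-sided 5% (sidedness assumed), 80% power: n per arm = 2 × (1.96 + 0.842)² × 6²/3² = 62.8, so 63 by the normal formula. With the t distribution, 64 per arm gives 80.1%. After 20% loss, 51 per arm gives 70.6%. The stated 64, 80% and 70% are reproduced, so 6 kg is the SD of 6-month change.

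**2. What autoregression on weight implies.** If weight has SD S and correlation r between adjacent visits, the SD of change over k intervals is S√[2(1 − rᵏ)]. Setting this to 6 kg at k = 1 gives r = 1 − 36/(2S²). S is not in the documents. For an assumed S = 25 kg:
- r = 1 − 36/1250 = 0.9712
- month 12: √[1250 × (1 − 0.9432)] = 8.4 kg
- month 18: √[1250 × (1 − 0.9161)] = 10.2 kg

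For S from 20 to 35 kg the results are 8.4-8.5 and 10.2-10.3 kg. Conditioning on baseline hardly changes this: S√(1 − r²ᵏ) gives 6.0, 8.3 and 10.0 kg at S = 25. So the plan's assumption about weight, combined with adjustment for baseline, implies unequal variances at the three follow-up visits.

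**3. Type I error of the equal-variance AR(1), baseline as covariate.** As a hand approximation with complete data, the model's month-18 SD is roughly the root mean square of the three visit SDs:

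| True SDs (kg) at 6/12/18 months | Pooled SD | Ratio to true month-18 SD | P(abs Z > 1.96 × ratio) |
|---|---|---|---|
| 6/8.5/10.4 | √(216.4/3) = 8.49 | 0.817 | 11% |
| 6/9/12 | √(261/3) = 9.33 | 0.777 | 13% |
| 6/12/12 | √(324/3) = 10.39 | 0.866 | 9% |

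Simulation (64 per arm, REML, arm-by-visit means, 1,500 trials per scenario) agrees: 13% for 6/9/12 and 8.5% for 6/12/12 with complete data, about 12-13% with missing-at-random dropout, and 5-6% without growth. Monte Carlo error is at most √(0.13 × 0.87/1500) = 0.9 points. Separate smaller runs of 6/8.5/10.4 gave 12% with complete data and 12-13% with about a quarter lost, with standard errors 19-25% too small. On that pattern an unstructured covariance gave 3% (400 trials) and 6-7% (500 trials, no small-sample degrees of freedom). That is scatter around 5%.

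**4. Bias, true effect −3 kg.** One fit with 60,000 per arm in each scenario. Assumed: lag-1 correlation 0.8 or random-walk correlation, about 10% dropout per interval, dropout depending on the last observed change.

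| Dropout | Estimate under equal-variance AR(1) | Bias |
|---|---|---|
| None | −2.9 to −3.1 | about 0.1 kg or less |
| Same rule in both arms | −2.8 to −3.0 | up to about 0.2 kg |
| Rule differs by arm | −2.1 to −2.3 | 0.7-0.9 kg |
| Opposite rules by arm (extreme) | −0.9 to −1.4 | 1.6-2.1 kg |

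Where AR(1) was the true structure, the estimate stayed at about −3.0 throughout.

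**5. Other readings of the text.** With AR(1) on weight and baseline as a response visit (3,000 trials), type I error was about 5% for 6/8.5/10.4, 7-8% for 6/9/12 and 4% for 6/12/12. With no growth (6/6/6) it was 1%, so that model is then conservative. With autoregressive correlation and a separate variance at each visit, it was about 3% (400 trials) and 4.7-5.5% (600 trials per scenario).

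**6. What the earlier trial says about spread** (Background, Weight management). SD = difference/t × √(n/2). With an assumed 63 per arm at both visits:
- 6 months: 1.8/2.285 × 5.61 = 4.4%
- 12 months: 5.6/2.858 × 5.61 = 11.0%, a ratio of 2.5

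The numbers analysed are not given. With 50-63 per arm at 6 months and 25-63 at 12 months, the ratio is 1.5-2.8. The responder rates do not confirm growth. If all randomized participants count and change is normal, the meal-plan SD is (5 − 2.3)/0.739 = 3.7% at 6 months and (5 − 0.6)/1.126 = 3.9% at 12 months, a ratio of 1.07. The 12-month eSLD figures (mean loss 6.2%, 36% reaching 5%) have no normal solution.

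**The case against.** The strongest reply is that the text does not fix the model that fails. It specifies a correlation structure, not equal variances, so a heterogeneous-variance autoregressive model would satisfy it and holds its error rate. It also places the structure on weight. If baseline is a response visit, even equal-variance AR(1) lets the spread of change grow, and the error rate stays at 4-8% in the growth scenarios. This stands. The defect is that the wording admits models ranging from valid to about 13% error and does not choose between them.

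A reader might also infer that the plan's own figures show the spread doubling after month 6, so that the p-values and the unbiasedness claim fail outright. The documents do not support that. The only SD is 6 kg at month 6. Any doubling is back-calculated from another trial's p-values, with the test and analysed numbers unstated. It reaches month 12 only, and the responder rates do not bear it out. Nor does unbiasedness simply fail: material bias needs outcome-dependent dropout that differs by arm, and the documents do not predict that. They do treat loss that differs by treatment as possible, since they plan to test for it.

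Finally, the 18-month t-test is named first and uses no covariance structure. That limits the reach of the point to the mixed model.

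**Conclusion.** The point holds as a specification gap in the 18-month mixed model and should be corrected. Confidence is high that missing at random alone does not secure unbiasedness and that no variance allowance or fallback is given. Confidence is moderate on size.

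The 8.5-13% error rate requires three things together: an equal-variance AR(1), baseline as covariate only, and spread that grows after month 6. The 0.7-0.9 kg bias requires, in addition, outcome-dependent dropout that differs by arm. The dropout model, the correlations and the later SDs are assumptions, not document figures. The 6-month primary t-test, the sample size and the 18-month t-test are unaffected.

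**What to change.** In Analysis plans, Secondary aim 1:

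- Replace the autoregressive assumption with an unstructured covariance for the 6-, 12- and 18-month weights. Use baseline weight as a covariate, keep arm-by-visit terms in the model whatever their significance, and use small-sample degrees of freedom.
- Name a heterogeneous-variance autoregressive structure as the fallback if the model does not converge.
- Reword the unbiasedness sentence so that it requires both missing at random and a correctly specified model.

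The cost is a few sentences and a changed covariance option in the code. Three follow-up visits need 3 × 4/2 = 6 covariance parameters instead of 2, so four more with 128 participants, and the fallback may be needed. Which 18-month analysis leads, the t-test or the mixed model, is a separate choice for the sponsor.

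### The 18-month responder comparison codes every missing weight as a failure, which biases the arm difference under the plan's own missing-at-random assumption if dropout is unequal

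*Combined protocol and SAP*

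**What the plan says.** Under Analysis plans, secondary aim 2 compares the proportion of each arm with at least 5% loss at 18 months. The comparison "will be evaluated using a chi-square test". The only missing-data instruction for it is "Participants without an 18 mo. weight will be classified as not meeting the" 5% goal. No reason and no sensitivity analysis are given.

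Secondary aim 1, just before it, uses the same 18-month weights and says: "We anticipate greater loss to follow-up over time; however, we expect data to be missing at random". It then relies on this: "Under this assumption, mixed linear models will provide unbiased treatment comparisons".

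The Missing Data/ imputation section says "missing data for analyses of the primary aim will be imputed". It also says "We will determine if the proportion of participants lost to follow-up differs by treatment", but the result of that check only steers the choice of imputation method. It does not change the handling of secondary aim 2.

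**The concern.** A participant with a missing 18-month weight is treated in aim 1 as predictable from observed data. In aim 2 the same participant is a certain failure, even if well below the 5% threshold at the 12-month visit. Coding missing as failure lowers each arm's response rate, so it is conservative for a single arm. It is not conservative for a difference between arms, because the arm with more missing weights loses more responders.

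Aim 2 is the only planned between-arm test of clinically significant weight loss. The plan expects loss to grow over time, so the 18-month visit is the most exposed. Depending on which arm loses more people, a real advantage could be inflated or hidden, or an apparent one created.

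**Working it through.** **Inputs from the documents.** The Power/sample size paragraph gives 64 per arm and a type 1 error of 0.05; sidedness is not stated and is taken as two-sided. Secondary aim 2 gives the failure rule and the chi-square test, taken as uncorrected. The only attrition figure is 20%, used for the 6-month completer power. There is no by-arm figure and no 18-month figure.

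**Assumptions.** No 18-month response rate is given. I use 35%, close to the 36% reported at 12 months for the eSLD arm of the group's earlier trial (Background), and 50% as an alternative. Dropout rates by arm are also assumed.

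**Step 1: the plan's own figure.** The plan sets out "To detect a clinically meaningful difference of 3 kg" with "type 1 error rate of 0.05, assuming a common standard deviation of 6 kg, will require 64 participants/group". Noncentral-t power for 3 kg and SD 6 kg is 80.1% at 64 per arm. At 51 per arm (64 × 0.8 = 51.2) it is 70.6%. The stated 64, 80% and 70% reproduce. No power is stated for the responder endpoint.

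**Step 2: what the rule does.** In arm k let p be true response, d the share without an 18-month weight, and r the true response among those dropouts. Then

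observed rate = p − d × r

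observed difference = (p₁ − p₂) − (d₁r₁ − d₂r₂)

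If dropouts respond like completers (r = p), the observed rate is p × (1 − d), and equal dropout multiplies the difference by (1 − d). If r = 0, the rule changes nothing.

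**Step 3: no true difference.** Exact binomial enumeration, 64 per arm, true response 35% in both arms:

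| Dropout | r = 35%: observed rates | Rejection | r = 17.5%: observed rates | Rejection |
|---|---|---|---|---|
| 15% / 20% | 29.8% / 28.0% | 5.7% | 32.4% / 31.5% | 5.3% |
| 15% / 25% | 29.8% / 26.3% | 7.4% | 32.4% / 30.6% | 5.6% |
| 10% / 30% | 31.5% / 24.5% | 14.5% | 33.3% / 29.8% | 7.2% |

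With r = 0 the rejection rate stays at about 5% in every row. With equal 20% dropout and r = 35% it is 5.1%. At 50% true response the 15/25 and 10/30 rows give 9.4% and 22.0% with r = 50%, and 5.8% and 8.6% with r = 25%.

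**Step 4: a true difference, with r = p.**
- True 50% vs 30%, 20% dropout in both arms: observed 40% vs 24%, so 20 points become 20 × 0.8 = 16. Power is 50% under the rule, 56% for completers (51 per arm) and 65% with complete data.
- True 50% (GR) vs 36% (IH), a difference of 14 points. GR/IH dropout of 10/30% gives 45.0 − 25.2 = 19.8 points. Dropout of 30/10% gives 35.0 − 32.4 = 2.6 points.

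**Step 5: does imputation repair it under missing at random?** A simulation (1,500 runs, 10 imputations) imputed the 18-month weight within arm and then applied the 5% cut. It assumed a 6/18-month correlation of 0.7 and an SD of 7% of baseline weight. With equal 36% response and 10/30% dropout, imputation rejected about 4% of the time with a mean difference near 0. The rule rejected about 15% with a difference of 32.4 − 25.2 = 7.2 points. For true 50% vs 36% with GR/IH dropout 30/10%, imputation recovered about 13.7 of the 14 points.

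**The case against.** The strongest reply is that the large figures come from letting dropouts respond like completers. People who leave a weight-loss trial may well do worse, and then the rule is nearer the truth. This stands: the half-response column in step 3 shows most of the inflation gone.

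The remedy can also err the other way. Take 35% true response, 10/30% dropout and dropouts responding at 10%. Completers then show (35 − 1)/0.9 = 38% vs (35 − 3)/0.7 = 46%. A completer chi-square rejects 12.9% of the time against 5.8% for the rule. Imputation from earlier weights removes only the part of this that those weights explain.

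The rule is also prespecified, keeps all randomised participants in the denominator, and could be defended as a composite of staying in and losing 5%. The plan does not define it as one.

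Several stronger readings are tempting but not supported:
- A reader might infer that aims 1 and 2 contradict each other. They are separate analyses with separate rules; only the assumptions about the same missing weights differ.
- A reader might infer that the test will in practice measure attendance. The documents predict no dropout gap and expect attrition below 20%. They plan equal contact, and home-visit weights taken by blinded staff in both arms.
- A reader might put any disagreement between the mean and responder results down to missing data alone. A mean and a 5% cut can disagree with complete data.
- A reader might take 65% to 50% as the power cost of the rule. The 65% is not attainable once weights are missing; against completers the loss is about 6 points.

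**Conclusion.** The point holds in a limited form. Under the missing-at-random assumption that the plan adopts for these weights, the failure rule biases the between-arm difference toward the better-retained arm, given similar response among dropouts in both arms. With equal dropout, type I error stays near 5% and the difference shrinks by the missing share if dropouts respond like completers.

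At 35% response, the inflation runs from none (no dropout responds) to a rejection rate of 14.5% (10/30% dropout, dropouts like completers). A 5-point dropout gap barely matters. Where the trial falls in this range cannot be read from the documents. The check of loss by treatment would reveal a gap, but nothing in the plan then changes the aim 2 analysis. This is a secondary endpoint, and the primary aim is unaffected.

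**What to change.** Extend the plan's multiple imputation to secondary aim 2. Impute the 18-month weight within arm from the measured baseline, 6-month and 12-month weights, apply the 5% cut in each imputed data set, and pool the risk difference. Report this together with the missing-as-failure result and the number without an 18-month weight in each arm. State in advance that a firm conclusion on the arm difference will be drawn only if the two results agree.

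Home-scale weights may enter the imputation model only if they are retained as study data. The documents describe the scales for self-monitoring and do not list them among the outcome measures.

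The cost is a paragraph of SAP text and one derived variable; the measured weights are already scheduled. The downside is that the imputed result rests on missing at random. It would overstate response if dropouts regain more than their earlier weights predict, which is why the failure-rule result stays beside it.
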